The relative approach (e.g. 5 or 10% intervals) performs well in regular sinus rhythm. In case of increased heart rate variability, atrial fibrillation, or ectopic beats, absolute reconstruction should be employed (e.g. 50 msec) in combination with ECG-editing if necessary.

CAVEAT: "Best Diastole" and "Best Systole" are algorithms which aim at automated identification of optimal reconstruction phases with the least coronary artery motion in Diastole or Systole. However, these algorithms are intended for coronary CTA and not aortic root imaging.

[figure not shown]
REVIEW OF DATA RECONSTRUCTION AND ECG-EDITING

- Image reconstructions of the aortic root and heart should be reviewed immediately after the scan when raw data is still available
- The ECG-gating should be reviewed to ensure that the automated algorithms correctly identified the R-peaks (dots, also known as "Syncs" should be aligned with R-peaks)
- If R-peaks were not correctly identified, manual correction should be performed (e.g. "Insert Sync" if an R-peak was not identified, or "Delete Sync" if a Sync was placed on anything other than the R-peak; alternatively Syncs can also be shifted manually)
- In case of ectopic contractions, absolute reconstruction should be used and the Sync of the ectopic beat should be deleted

- If mis-registration or stair-step artifacts are present, ECG-editing should be employed with either modification of trigger-points (if they were initially incorrectly identified by the algorithm) or deletion of trigger-points (in premature contraction or atrial fibrillation).

CT Acquisition and Reconstruction Techniques for Transcatheter Aortic Valve Procedure Planning Utilizing Toshiba Hardware

WRITTEN IN COLLABORATION WITH:

EDITED BY:
 [name], FSCCT
 Cardiac Imaging Specialist
 Center for Heart Valve Innovation
 St. Paul's Hospital & University of British Columbia
 Vancouver

[name] RN, BSN, RCIS
 Global Product Training Manager
 Imaging, Procedure, and Patient Initiatives
 Edwards Lifesciences, THV – Global

[name] R.T. (R)(CT)
 Marketing Clinical Support Specialist, CT
 Toshiba America Medical Systems

References

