Data Acquisition

[figure not shown]

Figure 1 – Retrospective ECG-gated helical data acquisition without dose modulation. The tube current (blue bar) is set at its peak during the entire cardiac cycle. The black boxes indicate the time point of image reconstruction within the cardiac cycle.

Retrospective ECG Gating (Spiral/Helical Mode)

- Helical data acquisition due to continuous movement of the patient through the gantry while the scanner gantry rotates
- Simultaneously records the ECG signal
- The recorded ECG signal allows for "retrospective" image reconstruction at specific time points of the cardiac cycle (FIGURE 1)

- In general, this technique is available on all scanner platforms capable of cardiac CT
- Advantage: Allows for dynamic (cine) imaging/ image reconstruction throughout the entire cardiac cycle (early systole – late diastole)
- Advantage: Greater flexibility in unstable heart rates or rhythms (eg, atrial fibrillation or premature ventricular contractions) – ability to use data from different phases (eg, systole or

- diastole) and to manually edit the reconstruction (please refer to ECG Editing)
- Disadvantage: Relatively high radiation dose, as full tube current is applied throughout the entire cardiac cycle

ECG Editing with Retrospective ECG Gating

- The in-part redundant image data which is acquired using retrospective ECG gating and helical data acquisition allows for manual editing of the ECG signal with adjustment or deletion of certain trigger points (eg, an entire heart beat may be deleted in case of a premature contraction)
- This technique should be employed in cases of misalignment artifacts due to premature contractions or atrial fibrillation
- ECG editing has to be performed at the scanner console using the raw data

CAVEAT: Raw data is commonly stored for a limited time only.

[figure not shown]

Figure 2 – Example of retrospective ECG gating with dose modulation during systole (not recommended). Images reconstructed during systole outside of the window of peak tube current are noisy and uninterpretable.

Data Acquisition

[figure not shown]

Figure 3 - Retrospective ECG-gated helical data acquisition with dose modulation. Peak tube current is limited to mid-diastole (not recommended). Image reconstruction at systole (lower row) will likely result in uninterpretable image quality.

Recommendation:

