- Ideally dose modulation should be switched off to allow for data acquisition with peak tube current throughout the entire cardiac cycle; however, if utilized, it is recommended that dose modulation be used only in diastole set to 20% – 30% peak dose
- It is not recommended, to use dose modulation in systole. *CAVEAT: Most automated coronary CTA protocols with dose modulation reduce tube current during systole.*
- ECG editing should be considered to reduce artifacts due to premature contractions or atrial fibrillation

Dose Modulation in Retrospective ECG Gating:

- Dose modulation is modulation of the tube current throughout the cardiac cycle with peak tube current (mAs) during a predefined phase of the cardiac cycle and lowered tube current during the remainder of the cardiac cycle (FIGURES 3 & 4)
- Although image reconstruction is still technically feasible throughout the cardiac cycle, images reconstructed outside the preselected phase

- will have increased image noise and may not be interpretable
- For aortic root evaluation, images are usually uninterpretable if tube current is lowered below one third of the peak current
- Due to the pulsatile and conformational changes of the aortic annulus throughout the cardiac cycle with larger dimensions usually found in systole, peak tube current is warranted during systole

Data Acquisition

[figure not shown]

Figure 4 - Retrospective ECG-gated helical data acquisition with dose modulation. Peak tube current is limited to systole. Image reconstruction at diastole (middle row) will likely result in uninterpretable image quality.

- Advantage: Dose reduction
- Disadvantage: Images reconstructed outside of the window of full/peak tube current have increased image noise and may be uninterpretable

[figure not shown]

Figure 5 – Prospective ECG-triggered sequential data acquisition. Upper row with diastolic data acquisition (not recommended), lower row with systolic data acquisition.

Prospective ECG Triggering (Sequential/Axial Mode)

- Data acquisition is prospectively triggered by the ECG signal (FIGURE 5)
- Data acquisition is performed in a slab-wise (axial, non-helical) fashion while the patient table does not move. The table is moved in between slabs
- Acquisition windows are usually limited to a specific portion of the cardiac cycle (eg, only mid-diastole) with no radiation exposure or image acquisition occurring outside of the acquisition window

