- Limitation of the acquisition window often allows for only one single reconstruction, or if the window is slightly broadened ("padding") for slight variation in the reconstruction window
- Advantage: Lower radiation dose
- Disadvantage: Allows for only limited coverage of the cardiac cycle and almost no correction in case of misregistration or motion artifact

Data Acquisition

Recommendation:

- If prospective ECG-triggering is employed, the acquisition window should be centered in systole.
- Due to the limited potential for image correction, this imaging technique should only be employed if radiation dose is a concern.

High-Pitch Helical Data Acquisition

- High-pitch data acquisition is limited to second and third generation dual-source scanners and employs high pitch factors of 3.2-3.4
- Data acquisition can be ECG triggered to aim for systolic or diastolic data acquisition at the level of the aortic root
- This technique allows only for a single reconstruction
- **Advantage:** Low radiation exposure
- **Disadvantage:** Allows for only a single reconstruction

CT Scan – Patient Preparations

- Positioning of the patient on the scanner table, typically supine, should closely resemble positioning on the cath lab table
- Placement of ECG electrodes and IV access should follow institutional policies
- Patient instruction on breath-holding prior to scanning may improve compliance with the breath-holding instructions during the scan

Note:

Volume scanners with wide z-axis coverage (eg, 256-slice or 320-slice CT scanners) may be capable of covering the entire aortic root with one slab using axial data acquisition and prospective triggering. By extending the acquisition window to cover the entire cardiac cycle, this technique may allow for dynamic imaging, and may then be considered equivalent to retrospective ECG-gating without dose modulation. However, given the prospective nature of the data acquisition, where redundant data is not acquired, ECG editing is not possible.

PARTNER 3
December 2015, Version 1.0

K1-9

[figure not shown]

Figure 6 – Scout views highlighting two different imaging strategies: Left, ECG-assisted data acquisition limited to the aortic root and heart (green box) followed by non-gated CTA of the thorax, abdomen and pelvis (purple box). Right, ECG-assisted data acquisition of the entire thorax (green box) followed by the non-gated CTA of the abdomen and pelvis (purple box).

CT Scan – Scan Length and Scan Strategy

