- Certain post-processing platforms facilitate annular segmentation by manual placement of seeding points at the identified hinge points. After placing a seeding point for all three cusps, the plane transecting all three points is automatically displayed.

Semi-automated Annular Segmentation

- Certain post-processing platforms perform an automated segmentation of anatomical landmarks, including the basal hinge points, allowing for an automated display of the annular plane

Note:

Confirmation of the correct identification of the annular plane is warranted for both the facilitated and semi-automated segmentation, ie, by "turning" the cross hairs and verifying the location of the hinge points on the long axis view.

PARTNER 3
December 2015, Version 1.0

K1-15

[figure not shown]

Figure 9 – Dynamic changes in annular dimensions and configuration throughout the cardiac cycle. Conformational changes occur due to bulging of the aorto-mitral junction (red dashes) towards the left atrium during systole.

Annular Plane

Importance of Cardiac Phase for Determining Maximum Aortic Annular Dimensions

- The aortic annulus is subject to pulsatile and deformational changes throughout the cardiac cycle
- The annular area may vary greatly between systole and diastole (FIGURE 9). Edwards sizing charts are based on maximum systolic area. Maximum systolic area is determined by evaluating the aortic annulus in 5 – 10% increments from 25 – 45% of the R – R interval.

PARTNER 3
December 2015, Version 1.0

K1-16

Measurements

After proper identification of the annular plane the annulus measurement and ancillary measurements should be performed.

These measurements can be grouped into measurements which depend on the annular plane and measurements which do not depend onto the annular plane.

Measurements Depending on Annular Plane

- Annular dimensions
- Prediction of fluoroscopic angulation
- Distance to coronary ostia (coronary artery height)
- Sinus height (sinotubular junction height)
- Left Ventricular Outflow Tract (LVOT)
- Ascending aorta length

Measurements Independent of Annular Plane

- Sinus of Valsalva width
- Sinotubular junction (STJ) diameter
- Ascending aorta diameter

Although several automated tools are commercially available to expedite the valve analysis workflow, it is important to understand the approach for each measurement in order to be capable of performing the assessment manually and to recognize errors which may occur in an automated analysis.

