General 
 ECG-gated data acquisition of the aortic root and heart Scan range: beginning 2 cm below the carina to the base of the heart Irregular heart rates (HRs) are frequent within the TAVR population. Using the HR override capability with manually setting the HR to a lower value yields a lower pitch value which results in redundant CT data acquisition and thus provides the greatest fill in image reconstruction (e.g. utilization of SnapShot Segment, SnapShot Burst or SnapShot Burst Plus) 	Data acquisition 
 Scan Mode: Cardiac Helical Scan Parameter: 
 < 80 bpm: SnapShot Segment > 80 bpm: SnapShot Burst DFOV: 25 cm HR Override: On (manually enter min HR present on the ECG trace) Rotation speed: 
 HR < 80 bpm: 0.40 seconds HR > 80 bpm: 0.35 seconds Tube voltage: 
 120 kVp for BMI > 25 kg/m² 100 kVp for BMI < 25 kg/m² Tube current (manual): 450/600/700 mA for small, average and large patients ECG Dose modulation is not recommended, alternatively ensure maximum mA in systole (e.g. 25 to 45%, R-peak delay 35%) TargetPhase reconstruction: 5-95% Slice/Collimation: 0.625mm Scan direction: cranio-caudal Pitch: Autopitch (determined by HR) Auto voice (Breath hold command): Inspiration only 	Data reconstruction 
 Axial multiphasic reconstruction covering the entire cardiac cycle, 5% or 10% intervals in sinus rhythm Use ECG editing if necessary Slice Thickness: 0.625 mm Increment: 0.62 mm Recon: Std Iterative reconstruction: ASiR (if available) 50%
		

 Keeping as many parameters the same in Group 1 and Group 2 will result in a faster transition between the gated and non-gated groups In particular the rotation time needs to be consistent. The non-gated Group 2 is limited to a rotation speed of 0.40 seconds. Thus for heart rates < 80 bpm, both groups should employ 0.40 seconds. For heart rates > 80 bpm, a rotation speed of 0.35 seconds should be used, however this leads to a longer transition time 		

Group 2 scan parameter – non-gated CTA of the thorax, abdomen, and pelvis		

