
General
 
 Single contrast application for both the retrospectively ECG-gated CTA of the aortic root/heart and the CTA of the thorax/abdomen/pelvis Placement of IV access in an antecubital vein (an 18-gauge IV typically provides the highest safety) Automated contrast injection using a dual-cylinder injector 	
Specific
 
 Contrast bolus monitoring and timing of data acquisition by means of bolus tracking at the level of the ascending aorta with a ROI placed within the ascending aorta; threshold set at 100 HU above baseline, delay to start of data acquisition after reaching threshold 7 sec

LOW-CONTRAST DOSE PROTOCOL - RATIONALE FOR ALL SCANNER TYPES

- Same scanner settings as listed above, except the threshold setting for bolus tracking
- Reduce scan length of the retrospectively ECG-gated CTA (#5) to a minimum to cover only the aortic root as opposed to the entire heart, as this is the time-intensive part in regard to data acquisition
- Injection rate might be lowered
- Threshold to trigger initiation of the retrospective ECG-gated spiral data acquisition can be lowered to 80 HU
- Systems with the capability of low kV data acquisition (70kV - 90kV, Force) may allow for reduced iodine delivery rates as low kV data acquisition increases iodine attenuation; CARE KV settings need to be adjusted (setting 4-7).

These alterations should allow for a sufficiently contrast-enhanced CT dataset of the aortic root. Contrast attenuation of the iliofemoral acquisition may be variable.

DOSE MODULATION FOR RETROSPECTIVE ECG-GATED SPIRAL DATA ACQUISITION

The protocols listed above do not employ dose modulation for the retrospective ECG-gated spiral data acquisition, allowing for image reconstructions throughout the entire cardiac cycle at a constant image noise level. This allows for identifying the reconstruction phase with largest annular dimensions and optimal image quality. If dose modulation is employed, peak dose should be applied during systole with a pulsing window set to 5 - 35%. MinDOSE should not be used, as this renders images non-interpretable outside of the pulsing window.

RECONSTRUCTION OF MULTIPHASIC DATA SET

[figure not shown]
Multiphasic ("dynamic", "cine") data sets can be reconstructed using a relative approach (percentage intervals [%] between two R-peaks) or an absolute approach (fixed distance of the reconstruction window from the R-peak, reported as [msec]).

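### Appendix K-1's optional Siemens dose-modulation window (5-35% R-R) covers only half of the 25-45% range over which the maximum annular area is to be found

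*Combined protocol and SAP*

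**What the plan says.** All of the relevant text is in Appendix K-1, the screening CT manual.

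- **Sizing phase.** The general section on cardiac phase says the sizing charts rest on maximum systolic area, which is determined by "evaluating the aortic annulus in 5 – 10% increments from 25 – 45% of the R – R interval". It gives the reason: "The annular area may vary greatly between systole and diastole".
- **General rule on dose modulation.** The preferred setting is no modulation. If modulation is used, current should be lowered only in diastole, to 20-30% of peak. For systole the text says: "It is not recommended, to use dose modulation in systole".
- **What low current does.** For the aortic root, "images are usually uninterpretable if tube current is lowered below one third of the peak current". The caption to Figure 2, an example marked as not recommended, says: "Images reconstructed during systole outside of the window of peak tube current are noisy and uninterpretable".
- **Siemens fallback.** Both Siemens protocol tables (Flash/Force and AS64/AS+) have pulsing switched off. The later Siemens section on dose modulation says that, if it is used nonetheless, "peak dose should be applied during systole with a pulsing window set to 5 - 35" percent. That section also bars MinDOSE, but it states no current level for the rest of the cycle.
- **GE fallback.** The table for the GE 64-slice family also advises against modulation, and then says: "alternatively ensure maximum mA in systole (e.g. 25 to 45%, R-peak delay 35" percent).

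**The concern.** The range used to find the maximum area ends at 45% of R-R, while full dose in the Siemens fallback ends at 35%. A site that follows both instructions therefore images the later part of the sizing range at reduced current. K-1's general section advises against exactly that, and its GE fallback avoids it. Nothing in the Siemens section explains the different window.

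The measurement matters because annular area feeds the sizing table (Table 5.1.1-1, section 5.1.1) and exclusion criterion 1 (section 7.2). The CT ranges for the 23 mm and 26 mm valves meet at 430 mm² without overlapping, so near that value a small shortfall in area could change the indicated size.

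The upload requirement in K-1 section 2.1, that systolic and diastolic volume sets be complete, would not reveal the problem. Under modulation every phase can still be reconstructed, only with more noise.

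**Working it through.** The plan gives no figure of its own to reproduce here. The check compares two windows and then prices the change.

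**Inputs.** From K-1: sizing range 25-45% R-R in steps of 5-10%; Siemens fallback peak-dose window 5-35%; GE fallback window 25-45%; interpretability level of one third of peak current; general out-of-window level of 20-30% of peak. That last figure is given for diastole only, so using it for Siemens is an assumption.

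**Overlap.**
- Siemens: min(45, 35) − max(25, 5) = 35 − 25 = 10 points. The sizing range is 45 − 25 = 20 points, so coverage is 10/20 = 50%.
- GE: 45 − 25 = 20 points, so coverage is 20/20 = 100%.

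**Phases at and below peak dose in the Siemens fallback** (35% counted as inside; ramp times ignored).

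| Phases read | At peak | Reduced current |
|---|---|---|
| 25, 30, 35, 40, 45 | 25, 30, 35 | 40, 45 (2 of 5) |
| 25, 35, 45 | 25, 35 | 45 (1 of 3) |
| 30, 40 | 30 | 40 (1 of 2) |

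**Are the reduced-current phases readable?** One third of peak is 33.3%. At the assumed 20-30% they fall below that level and would usually not be interpretable. Above one third they may be. The Siemens text bars MinDOSE, which Appendix K-2 describes as 4% of peak, but sets no floor.

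**Direction of error.** A maximum over a subset of phases is at most the maximum over all of them. If 40% and 45% are discarded, the area can equal the true maximum or fall short of it, but cannot exceed it apart from reading error. If they are read despite the noise, contour error can go either way and the loss is one of precision.

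**Dose cost of widening.** Let w be the fraction of R-R at peak and f the out-of-window current as a fraction of peak. Cycle-average current relative to peak is w + (1 − w)f.

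| Window | w | f = 0.20 | f = 0.30 |
|---|---|---|---|
| 5-35% | 0.30 | 0.30 + 0.70 × 0.20 = 0.44 | 0.30 + 0.70 × 0.30 = 0.51 |
| 5-45% | 0.40 | 0.40 + 0.60 × 0.20 = 0.52 | 0.40 + 0.60 × 0.30 = 0.58 |
| 25-45% | 0.20 | 0.20 + 0.80 × 0.20 = 0.36 | 0.20 + 0.80 × 0.30 = 0.44 |

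For 5-45% against 5-35% the ratios are 0.52/0.44 = 1.18 and 0.58/0.51 = 1.14. For 25-45% against 5-35% they are 0.36/0.44 = 0.82 and 0.44/0.51 = 0.86. The unmodulated scan is 1.0.

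**The case against.** The strongest reply is that this is a fallback few sites need use. Pulsing is off in both Siemens tables, the Siemens paper is labelled educational reference, and the sponsor endorses no single protocol in it. The Siemens section itself explains that scanning without modulation is what lets the reader find the phase with the largest annulus. Barring MinDOSE suggests that usable images outside the window are intended. K-1 also asks for immediate review of reconstructions while raw data exist, lists image noise as a troubleshooting item, and wants screenshots that show image quality. All screening CTs are measured by a core lab (section 12.4.2), and sizing is reviewed by the Case Review Board (section 8.1.2). All of this stands and keeps the point small. It does not explain the 5-35% setting, and later review cannot restore current that was never applied.

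Three stronger readings are tempting, and the documents do not support them.

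- A reader might infer that 40-45% is unreadable. The residual current is not stated, the 20-30% level comes from a diastole-only rule, and the Figure 2 caption describes one discouraged example.
- A reader might infer that any error must make the annulus look smaller. That follows only if the noisy phases are discarded.
- A reader might extend the point to high-pitch scanning, of which K-1 says "Data acquisition can be ECG triggered to aim for systolic or diastolic data acquisition at the level of the aortic root", or to prospective triggering. K-1 describes high pitch and states its single-reconstruction limit, the Siemens Flash/Force table uses it only for the access CTA, and the upload requirement would screen out a single-phase scan. Prospective triggering is already to be centred in systole and kept for patients in whom dose is a concern.

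**Conclusion.** The inconsistency is real and minor. Within one appendix, the range for finding the maximum area and the Siemens fallback's peak-dose window overlap by half, which leaves 2 of 5 phases at 5% steps, or 1 of 3 at 10% steps from 25%, at reduced current. This runs against K-1's own advice on systole and differs from its GE fallback. The consequence is either a maximum that may be missed or one measured less precisely.

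The windows and phase counts come directly from the text. Whether the affected phases are unusable depends on an out-of-window current that the documents do not give. They also do not say how often the fallback is used or how large any area shortfall would be, so no number of mis-sized patients can be claimed. No endpoint definition, sample size, power or alpha figure is affected.

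**What to change.** In the Siemens section of Appendix K-1 on dose modulation, replace the 5-35% pulsing window with one that covers 25-45% of R-R: either 5-45%, or 25-45% to match GE. Leave the default of no modulation, the bar on MinDOSE and the upload requirement as they are. No change is needed to the high-pitch or prospective-triggering text.

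The cost is one changed setting in the manual. With 5-45%, cycle-average current rises by about 14-18% over the present fallback, to 0.52-0.58 of peak, if out-of-window current is 20-30% of peak. With 25-45% it falls by about 14-18%, to 0.36-0.44, but 5-25% of R-R is then no longer at full dose. The choice between the two can be left to the CT core lab.
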